**Secondary Outcome Measures:**

- Incidence of postoperative leakage requiring intervention through 30-day post-operative evaluation period
- Incidence of intraoperative or postoperative blood transfusion within 72 hours of surgery start time
- Hemoglobin difference between preop hemoglobin and hemoglobin on postoperative day #1 as well as difference between hemoglobin at recovery room and postoperative day #1
- Incidence of reported device-related adverse events through 30-day post-operative evaluation period
- Incidence of product malfunction during stapling
- Total hospitalization time
- Postoperative pain level per standard protocol (0-10 VAS scale completed at Recovery room, 6hrs postop and 7am at POD#1)
- Postoperative nausea presence (0-10 scale VAS completed at Recovery room, 6hrs postop and 7am at POD#1)
- Incidence of vomiting: incidence (at least one per patient) per stapler group, total episodes per group and emesis material (bloody or non-bloody)
- Correlation of number of reloads used and specimen lengths and maximum widths as measured by pathology examination
- Correlation of reload color used with observed bleeding and patient's stomach thickness by path exam
- Correlation of outcome parameters with BMI, visceral fat, gender and age
- Need for clipping the staple line prior to completion of the staple line

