### **Steps and Procedures:**

The study will include 60 total consecutive cases, randomized for stapler type: 30 with the AEON™ Endostapler and 30 with Endo GIA™ Reloads with Tri-Staple™ Technology. Surgeries will be performed by [name].

All patients will undergo the standard preoperative evaluation pathway. Patients must sign informed consent for the operation.

All firings with the AEON™ Endostapler will be done with THICK MODE for the purposes of this study and shall conform to the AEON™ Instructions for Use. All firings with the Endo GIA™ Reloads with Tri-Staple™ Technology and Ultra Universal Handle should be done according to the Endo GIA™ Instructions for Use.

To measure incidence and degree of staple line bleeding, a third-party blinded evaluator will be used. No sutures, cautery or clips shall be applied during stapling for staple line bleeding, unless required at surgeon's discretion. Following the last firing, a member of the surgical or nursing team or the research coordinator present for the case will count 10 seconds and then capture images with the laparoscope. If bleeding from the staple line requires control prior to the last firing, an additional image should be captured before applying sutures, cautery, clips, etc. Five pictures will be obtained from each case: the pylorus, distal sleeve near the distal end of the staple line, mid-sleeve at the incisura angularis, proximal sleeve and GEJ near the proximal end of the staple line. These photographs will be sent by the research coordinator to the third-party evaluator either electronically or by mail. The third-party evaluator will be blinded to the device of each case. Upon receipt of photographs, the evaluator will evaluate staple line bleeding according to a provided Bleeding Severity Scale for Laparoscope Images (Appendix A) and record results in the Bleeding Severity Evaluation Sheet (Appendix E).

At the end of each case, the surgical team will fill out the relevant sections of the Data Collection Sheet (Appendix C).

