Gastroscopy will be performed, per standard protocol, at the beginning of the case to suction all gastric contents and decompress the stomach as well at the completion of the sleeve gastrectomy. Evaluation for intraluminal bleeding will be performed at the last gastroscopy according to Appendix E. During the last gastroscopy, no suctioning of the gastric contents will be performed until evaluation for bleeding is made and pictures are obtained. The gastroscopy will be performed before any use of clipping at the staple line unless for circumstances judged by the surgeon to be medically necessary to do so before the endoscopy. These instances will also be recorded. Five pictures will be obtained from each case: the pylorus, distal sleeve near the distal end of the staple line, mid-sleeve at the incisura angularis, proximal sleeve and GEJ near the proximal end of the staple line. These photographs will also be sent to the third-party evaluator for evaluation of staple line bleeding according to a provided Bleeding Severity Scale for Endoscope Images (Appendix B). Results will be recorded in the Bleeding Severity Evaluation Sheet (Appendix E).

The determination of laparoscopic and endoscopic staple line bleeding will be based on the picture with the highest bleeding severity score for laparoscopic and endoscopic evaluation separately. Every effort will be made that all pictures prior to any suctioning of the staple line laparoscopically or endoscopically.

All typical post-operative care will continue, including immediate post-operative care prior to hospital discharge as well as the standard post-operative evaluation. A hemoglobin level will be checked at the

recovery room and at 5am on postoperative day #1 per standard protocol. This hemoglobin must be drawn from the upper extremity opposite from the one with the IV running fluids or at the same extremity with the IV running fluids but distal to the IV. For each post-operative period, a member of the surgical or nursing team will fill out the relevant sections of the Data Collection Sheet (Appendix C).

There will be no follow up study data collected after this point, however the patients will continue the standard follow up regimen per the physician's practice.

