### Intraoperative Outcomes

Product malfunction during stapling? (circle one)	Yes	No
Blood transfusion due to staple line bleeding? (circle one)	Yes	No
Visceral fat:		
Clips required for bleeding (non-routine)? (circle one)	Yes	No

*If yes to any above, please specify:*

Postoperative Outcomes				
	Pre-op	Recovery	6 Hours	POD #1
Pain level per standard protocol (0-10 VAS scale):	N/A			
Nausea level per standard protocol (0-10 VAS scale):	N/A			
Hemoglobin:			N/A	
72 Hours				
Blood transfusion due to staple line bleeding? (circle one)	Yes		No	
30 Days				
Total hospitalization time:				
Number of vomiting episodes:		Bloody	Non-bloody	
Reported device-related adverse events? (circle one)	Yes		No	
Postoperative leakage requiring intervention? (circle one)	Yes		No	

*If yes to any above, please specify:*

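### The outcome for control of staple line bleeding counts clips only, although sutures and cautery are also allowed, and its time window cannot be reliably derived from the data sheet

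*Combined protocol and SAP*

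**What the plan says.** The last item under Secondary Outcome Measures is "Need for clipping the staple line prior to completion of the staple line". It names one method and one early window.

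Steps and Procedures treats three methods alike: "No sutures, cautery or clips shall be applied during stapling for staple line bleeding, unless required at surgeon's discretion". If control cannot wait for the last firing, "an additional image should be captured before applying sutures, cautery, clips, etc". The Summary states that the investigator is not masked, so the method is chosen by someone who knows the stapler.

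The gastroscopy paragraph of the same section places the final endoscopy "as well at the completion of the sleeve gastrectomy" and sets the order: "The gastroscopy will be performed before any use of clipping at the staple line unless for circumstances judged by the surgeon" to require it sooner on medical grounds. It adds that such early instances are to be recorded.

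Appendix C, under Intraoperative Outcomes, has one yes/no item on local control, which begins "Clips required for bleeding (non-routine". It has no time limit, no field for timing, and no item for suture or cautery. The free-text line below it is prompted only by a yes to one of the items above.

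**The concern.** Staple line bleeding is the subject of the trial, and this is the only listed outcome on local control of it. A reader will take it as a measure of how often bleeding had to be dealt with before the line was finished. As defined, it measures how often the surgeon reached for a clip. The two agree only if clips are the method in nearly every case, or in the same proportion of cases in both arms, and the plan secures neither.

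The gap cannot be repaired at analysis. A patient treated by cautery or suture alone is a no on the clip item, so nothing on the sheet prompts a note. The duty to record in the gastroscopy paragraph covers clipping only. The extra photograph taken before early control has no row in Appendix E, so it does not serve as a count either.

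**Working it through.** The documents give no figure on this point, so there is none to reproduce. The check sets the passages side by side and then shows by arithmetic what follows. I take completion of the staple line to mean the last firing.

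**1. What each place counts**

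| Place | Methods | Window |
|---|---|---|
| Secondary Outcome Measures | clip | before completion of the staple line |
| Steps and Procedures, laparoscopic images | clip, suture, cautery (extra image, no count) | before the last firing |
| Steps and Procedures, gastroscopy | clip | before the final endoscopy |
| Appendix C, Intraoperative Outcomes | clip, non-routine, for bleeding | none stated |

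Consider three patients.
- Cautery or suture only, before the last firing: a non-event in the outcome and a no in Appendix C.
- Clip for bleeding between the last firing and the endoscopy: a non-event in the outcome, to be recorded under the gastroscopy text, and a yes in Appendix C.
- Clip for bleeding after the endoscopy: a non-event in the outcome and a yes in Appendix C.

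A yes in Appendix C therefore does not show whether the outcome occurred. Only a voluntary remark on the free-text line could.

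**2. Share of interventions not counted**

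Let c be the share of bleeding-control interventions that are clips, and t the share of those clips placed before completion. Neither is in the documents; the values below are assumptions.

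- Outcome as defined: share missed = 1 − c × t
- Appendix C item as printed: share missed = 1 − c

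| c | t | Counted, c × t | Missed by the outcome | Missed by Appendix C |
|---|---|---|---|---|
| 0.9 | 0.9 | 0.81 | 19% | 10% |
| 0.7 | 0.7 | 0.49 | 51% | 30% |
| 0.5 | 0.5 | 0.25 | 75% | 50% |
| 0.9 | 0.2 | 0.18 | 82% | 10% |

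More than half are missed only when c × t is below 0.5.

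**3. Effect of method choice on the comparison**

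The arms have 30 patients each (Steps and Procedures). Assume that all control is early and that each patient is treated by one method.

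- Equal need, different method: 9 of 30 in each arm, clips for two thirds against one third. The outcome reads 9 × 2/3 = 6 against 9 × 1/3 = 3.
- Different need, different method: 12 of 30 against 6 of 30, clips for one third against two thirds. The outcome reads 12 × 1/3 = 4 against 6 × 2/3 = 4.

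The first case creates a difference that is not there; the second hides one that is.

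**The case against.** A reader might infer that most interventions are missed, because clipping is by default put off until after the endoscopy and so falls outside the window. The documents do not support that. They give no rate by method or by timing, and at c = t = 0.9 only 19% are lost. Nor are later clips necessarily treatment for bleeding: the term non-routine in Appendix C implies that some clipping is routine.

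For the same reason the early window may be deliberate, as a way to isolate clipping that could not wait. That is a fair defence of the window. It does not explain leaving out suture and cautery, which the procedures name beside clips for the same purpose in the same period.

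Appendix C does pick up later clips for bleeding, and the gastroscopy text requires early clipping to be noted. Both points stand, and they narrow the loss in the data collected. They do not reach suture or cautery, and they give the analyst two further windows that differ from the outcome's.

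It would also be too strong to say that no other outcome records treatment in theatre, since intraoperative transfusion is both an outcome and a data-sheet item. Bleeding itself is graded by a blinded evaluator as the primary outcome, and the extra image is meant to catch bleeding before it is treated. This limits the damage to a secondary outcome. The Statistics section gives non-inferiority as the study's purpose, but no margin is set and nothing ties that conclusion to this item, so I do not claim that a low count here would be read as equivalence.

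**Conclusion.** The point holds in this form. The outcome counts clips only, although the unmasked surgeon may use suture or cautery instead. Patients controlled by those methods are non-events in both the outcome and Appendix C, so a difference in method between arms can change the result in either direction. The three recording windows for clips disagree, and without a timing field the outcome cannot be reliably derived from the sheet.

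The size of the loss is unknown. It ran from 19% to 82% over the values tried, all of them assumed, and the 6 against 3 and 4 against 4 examples also rest on assumed need and method shares. They show that the rule permits distortion, not that it will occur. The correction is worth making because it is cheap and because a method that goes unrecorded in theatre may not be recoverable later.

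**What to change.** Redefine the outcome as any clip, suture or cautery applied to the staple line for bleeding during the operation, with routine clips excluded. Keep the count before completion of the staple line as a component reported separately, by arm and by method.

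Replace the clip item in Appendix C with two fields for each intervention:
- method: clip, suture, cautery or other;
- timing: before the last firing, from last firing to gastroscopy, or after gastroscopy.

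Use the same windows in Secondary Outcome Measures, in the gastroscopy paragraph of Steps and Procedures and in Appendix C. A row in Appendix E for the extra image taken before early control would close the related gap.

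The cost is one reworded secondary outcome and one extra row on a sheet that the team already completes, plus the row in Appendix E if added. One weakness remains: for later clips, the unmasked surgeon still judges whether a clip is routine or for bleeding. That is why the early component should be reported on its own. Surgical management is unchanged.

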### **Steps and Procedures:**

The study will include 60 total consecutive cases, randomized for stapler type: 30 with the AEON™ Endostapler and 30 with Endo GIA™ Reloads with Tri-Staple™ Technology. Surgeries will be performed by [name].

All patients will undergo the standard preoperative evaluation pathway. Patients must sign informed consent for the operation.

All firings with the AEON™ Endostapler will be done with THICK MODE for the purposes of this study and shall conform to the AEON™ Instructions for Use. All firings with the Endo GIA™ Reloads with Tri-Staple™ Technology and Ultra Universal Handle should be done according to the Endo GIA™ Instructions for Use.

To measure incidence and degree of staple line bleeding, a third-party blinded evaluator will be used. No sutures, cautery or clips shall be applied during stapling for staple line bleeding, unless required at surgeon's discretion. Following the last firing, a member of the surgical or nursing team or the research coordinator present for the case will count 10 seconds and then capture images with the laparoscope. If bleeding from the staple line requires control prior to the last firing, an additional image should be captured before applying sutures, cautery, clips, etc. Five pictures will be obtained from each case: the pylorus, distal sleeve near the distal end of the staple line, mid-sleeve at the incisura angularis, proximal sleeve and GEJ near the proximal end of the staple line. These photographs will be sent by the research coordinator to the third-party evaluator either electronically or by mail. The third-party evaluator will be blinded to the device of each case. Upon receipt of photographs, the evaluator will evaluate staple line bleeding according to a provided Bleeding Severity Scale for Laparoscope Images (Appendix A) and record results in the Bleeding Severity Evaluation Sheet (Appendix E).

At the end of each case, the surgical team will fill out the relevant sections of the Data Collection Sheet (Appendix C).

Gastroscopy will be performed, per standard protocol, at the beginning of the case to suction all gastric contents and decompress the stomach as well at the completion of the sleeve gastrectomy. Evaluation for intraluminal bleeding will be performed at the last gastroscopy according to Appendix E. During the last gastroscopy, no suctioning of the gastric contents will be performed until evaluation for bleeding is made and pictures are obtained. The gastroscopy will be performed before any use of clipping at the staple line unless for circumstances judged by the surgeon to be medically necessary to do so before the endoscopy. These instances will also be recorded. Five pictures will be obtained from each case: the pylorus, distal sleeve near the distal end of the staple line, mid-sleeve at the incisura angularis, proximal sleeve and GEJ near the proximal end of the staple line. These photographs will also be sent to the third-party evaluator for evaluation of staple line bleeding according to a provided Bleeding Severity Scale for Endoscope Images (Appendix B). Results will be recorded in the Bleeding Severity Evaluation Sheet (Appendix E).

The determination of laparoscopic and endoscopic staple line bleeding will be based on the picture with the highest bleeding severity score for laparoscopic and endoscopic evaluation separately. Every effort will be made that all pictures prior to any suctioning of the staple line laparoscopically or endoscopically.

All typical post-operative care will continue, including immediate post-operative care prior to hospital discharge as well as the standard post-operative evaluation. A hemoglobin level will be checked at the

recovery room and at 5am on postoperative day #1 per standard protocol. This hemoglobin must be drawn from the upper extremity opposite from the one with the IV running fluids or at the same extremity with the IV running fluids but distal to the IV. For each post-operative period, a member of the surgical or nursing team will fill out the relevant sections of the Data Collection Sheet (Appendix C).

There will be no follow up study data collected after this point, however the patients will continue the standard follow up regimen per the physician's practice.

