**Primary Outcome Measure:**

- Incidence of intraoperative staple line bleeding from endoscopic or laparoscopic images as measured by the provided bleeding severity scale

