## Appendix E – Bleeding Severity Evaluation Sheet

Evaluation Date: \_\_\_\_\_ Evaluator: \_\_\_\_\_

Case #	Staple Line Image from Laparoscope	Staple line bleeding per Bleeding Severity Scale (choose one):				
		No bleeding	Minimal bleeding	Moderate bleeding	Excessive bleeding	Profuse bleeding
	A. Pylorus	1	2	3	4	5
	B. Distal sleeve near distal end	1	2	3	4	5
	C. Distal sleeve	1	2	3	4	5
	D. Proximal sleeve	1	2	3	4	5
	E. GEJ near proximal end	1	2	3	4	5

Case #	Staple Line Image from Endoscope	Staple line bleeding per Bleeding Severity Scale (choose one):				
		No bleeding	Minimal bleeding	Moderate bleeding	Excessive bleeding	Profuse bleeding
	F. Pylorus	1	2	3	4	5
	G. Distal sleeve near distal end	1	2	3	4	5
	H. Distal sleeve	1	2	3	4	5
	I. Proximal sleeve	1	2	3	4	5
	J. GEJ near proximal end	1	2	3	4	5

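### Appendix C does not capture the transfusion and clipping outcomes as defined, and the plan leaves unstated that the pre-control laparoscopic image is scored

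*Combined protocol and SAP*

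**What the plan says.** **Transfusion.** Secondary Outcome Measures counts transfusions during or after the operation up to 72 hours from the start of surgery, with no restriction on cause. Appendix C has two yes/no items, one intraoperative and one at 72 hours. Both are limited to transfusion attributed to staple line bleeding.

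**Clipping.** The same list includes clipping that was needed before the staple line was complete. Appendix C has one yes/no item, on non-routine clips for bleeding. A free-text line follows for any Yes answer. Steps and Procedures adds that clips placed before the final gastroscopy, where medically necessary, will be recorded.

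**Pre-control image.** If staple line bleeding has to be controlled before the last firing, Steps and Procedures says "an additional image should be captured before applying sutures, cautery, clips". It continues "Five pictures will be obtained from each case", lists five sites, and then says "These photographs will be sent by the research coordinator to the third-party evaluator either electronically or by mail". The case result is "based on the picture with the highest bleeding severity score for laparoscopic and endoscopic evaluation separately". The primary outcome is "Incidence of intraoperative staple line bleeding from endoscopic or laparoscopic images", measured on the severity scale. Appendix E has five laparoscope rows, A to E, ending at "E. GEJ near proximal end". The endoscope rows begin at F.

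**The concern.** A form narrower than the outcome it serves loses data without anyone noticing. A transfusion given for a reason other than the staple line is correctly answered No on Appendix C, yet it is an event under the outcome definition. For clipping, the form records the reason while the outcome depends on the time.

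The image gap matters for a different reason. The surgeon is not masked (Summary) and decides when bleeding needs control. The extra image preserves evidence that control will remove. If only the pictures taken after the last firing were scored, a bleed already controlled could be rated as no bleeding in the laparoscopic part of the primary outcome.

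**Working it through.** The documents give no figure to reproduce here: no expected bleeding, transfusion or clipping rate, and no margin or sample size calculation. The check sets text against form and then bounds the effect.

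**Step 1. Outcome against form**

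| Item | Outcome as defined | What Appendix C records | Lost |
|---|---|---|---|
| Transfusion | Any cause, up to 72 h from surgery start | Staple line bleeding only | Transfusions for other causes (answered No) |
| Clipping | Placed before staple line completion | Non-routine clips for bleeding, no time | Whether each Yes was before or after completion |

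The free-text line does not repair the transfusion item, because it applies only to Yes answers. For clips, suppose an arm has k Yes answers. The number clipped early can then be anything from 0 to k unless the free text or another record gives the timing.

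Size for transfusion: with 30 per arm (Steps and Procedures), each unrecorded transfused patient lowers that arm's incidence by 1/30 = 3.3 points. The number of such patients cannot be derived from the documents.

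**Step 2. Image rows**

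- Laparoscopic rows on Appendix E: 5 (A to E). Endoscopic rows: 5 (F to J). Total 10, with continuous lettering, so no row appears to be missing.
- Laparoscopic images in a case with early control: at least 5 + 1 = 6.
- So at least one image has no row of its own. It could be scored in the row for its site, but no text says so.

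**Step 3. Bound on the laparoscopic incidence**

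Assumptions: 30 cases per arm are analysed; a case counts as bleeding if its highest score exceeds 1 (the no-bleeding category on Appendix E); the extra image is not scored; none of the five later laparoscopic pictures shows bleeding.

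- Shift for m such cases in one arm: m/30. For m = 1, 2, 3 this is 3.3, 6.7 and 10.0 points.
- If equal numbers are missed in both arms, the difference between arms does not change.

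**Step 4. Offset by endoscopy**

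If the primary outcome counts bleeding on either image type, let e be the assumed share of these cases still scored as bleeding on endoscopy. The shift per case is 3.33 × (1 − e):

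- e = 0: 3.3 points
- e = 0.5: 1.7 points
- e = 1: 0 points

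**Step 5. Scale**

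The Newcombe 95% interval for a difference of zero has half-width √[(p − L)² + (U − p)²], where L and U are the Wilson limits for one arm of 30.

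- Assumed 3/30 in each arm: L = 0.035, U = 0.256, half-width √(0.065² + 0.156²) = 16.9 points.
- Assumed 15/30 in each arm: L = 0.332, U = 0.668, half-width √(0.168² + 0.168²) = 23.8 points.

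One omitted case is therefore 3.33/23.8 = 14% to 3.33/16.9 = 20% of the half-width. This shows scale only. It is not evidence that the omission will occur.

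**The case against.** **The image is already covered.** The instruction sits in the paragraph that opens by assigning bleeding assessment to the blinded evaluator, and no other use is given for the image. The highest-score rule is not limited to the five site pictures, and a pre-control image has a site whose row could hold its score. This largely stands: inclusion is the natural reading. A reader might infer that the plan excludes these bleeds, or that the primary comparison is biased. The documents do not support that. They contain no exclusion, no frequency and no basis for an imbalance between arms. What remains is that the sentence sending the photographs directly follows the one about five pictures, and the form has exactly five rows.

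**Early clips will be recorded anyway.** Steps and Procedures does promise a record of clips placed before the final gastroscopy, so it would be wrong to infer that their capture is left to chance. But that gastroscopy follows completion of the sleeve, so the record also takes in clips placed after the staple line was complete. The presence of an extra image does not separate them either, because the image may precede sutures or cautery instead of clips.

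**Row labels.** The text's third site is "mid-sleeve at the incisura angularis", while the third row reads "C. Distal sleeve"; row H has the same label. A reader might infer that mid-sleeve bleeding goes unscored. It need not: the rows follow the order of the listed sites, and relabelling a row does not change the maximum. This is clerical.

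**Sutures and cautery.** Appendix C has no item for them, but no listed outcome needs one, so this is not a mismatch.

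**Conclusion.** The point holds as a minor one. The transfusion mismatch is clear: following Appendix C as printed gives a narrower outcome than the one defined. Clip timing, on which the clipping outcome depends, has no field, and the promised record of clips before gastroscopy does not supply it. Both are confined to secondary outcomes.

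The image point touches the primary outcome but is an ambiguity, not a stated exclusion. The upper bound in one arm is 3.3 points of laparoscopic incidence per affected case. It requires early control, a literal reading of the text, and no bleeding on any later laparoscopic picture. The number of such cases is unknown and may be zero, and the endoscopic images may remove some or all of the effect.

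**What to change.** 1. On Appendix C, record any transfusion within 72 hours of the start of surgery, with cause as a separate field.
2. On Appendix C, record whether clips were applied before or after completion of the staple line.
3. In Steps and Procedures, state that the pre-control image goes to the blinded evaluator with the others and counts toward the highest laparoscopic score. Add a line for it, with its site, to Appendix E.
4. As a clerical correction, make the labels of rows C and H agree with the text.

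The cost is a few form edits and about two sentences of protocol text. The image is already called for, so no procedure, visit or analysis is added, and the surgeon's discretion over bleeding control is unchanged.

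### Between the last firing and the final gastroscopy pictures, only clipping is deferred and recorded; cautery or suturing in that interval could lower the endoscopic bleeding score

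*Combined protocol and SAP*

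**What the plan says.** Steps and Procedures covers control of the staple line in two stages.

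- **Up to the last firing.** All three measures are restricted together: "No sutures, cautery or clips shall be applied during stapling for staple line bleeding, unless required at surgeon's discretion". If control is needed before the last firing, an extra image is to be captured first, whichever measure is used.
- **After the last firing.** The team is to "count 10 seconds and then capture images with the laparoscope". The final gastroscopy comes at the completion of the sleeve. For this stage the rule is: "The gastroscopy will be performed before any use of clipping at the staple line unless for circumstances judged by the surgeon to be medically necessary". The plan adds "These instances will also be recorded", which refers back to clipping done early.

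The other protections of the endoscopic reading concern suction. A first gastroscopy is done "at the beginning of the case to suction all gastric contents and decompress the stomach". At the last one, "no suctioning of the gastric contents will be performed until evaluation for bleeding is made and pictures are obtained". A general sentence adds: "Every effort will be made that all pictures prior to any suctioning of the staple line laparoscopically or endoscopically".

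The bleeding result for each case is the picture with the "highest bleeding severity score for laparoscopic and endoscopic evaluation separately". The Primary Outcome Measure draws on both image sources.

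Appendix C has a yes/no row for non-routine clips and none for cautery, sutures or timing. Its free-text line is prompted only by a yes to a listed item. Appendix E has no treatment field. The Secondary Outcome Measures count clipping only, and only before the staple line is complete. The Summary states that the investigator is not masked.

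**The concern.** The plan's own text treats sutures, cautery and clips as alternatives for the same purpose until the last firing, and then names only one of them. The plan gives no reason for deferring clipping until after gastroscopy. If the reason is that controlling the line changes what the endoscope shows, it applies equally to the other two measures.

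Masking the evaluator protects the reading of each picture. It does not protect what was done to the line before the picture was taken, and the person deciding that knows the device. If cautery or suturing in this interval differed between arms, the endoscopic comparison could be distorted. Because neither the measure nor its timing is captured on the study form, the trial dataset would not show that this had happened.

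**Working it through.** The plan states no figure on this point, so the check is to set the rules side by side and ask which cases stay exposed.

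**Coverage of each measure**

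| Measure | Restricted during stapling | Extra image if used before last firing | Deferred until after gastroscopy | Row in Appendix C |
|---|---|---|---|---|
| Clips | yes | yes | yes, with exception | yes, without timing |
| Sutures | yes | yes | no | no |
| Cautery | yes | yes | no | no |

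The first two columns stop applying at the last firing. From then until endoscopic images F to J in Appendix E, no sentence restrains cautery or suturing.

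**Which lines are exposed**

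1. *Bleeding both outside and inside at the last firing.* Laparoscopic images A to E are taken at 10 seconds and should show the external bleed. Treatment afterwards can lower only the endoscopic score.
2. *Bleeding that appears after the 10-second laparoscopic pictures.* The laparoscopic score misses it, and treatment before gastroscopy can lower the endoscopic score as well.
3. *Prophylactic cautery or suturing of a line that looks dry.* The laparoscopic score is unaffected. The endoscopic score could be lower than it would otherwise have been.
4. *Bleeding visible only in the lumen.* It is first seen at the final gastroscopy, so little would prompt treatment before then unless the treatment is prophylactic (case 3).

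In cases 1 to 3, blood already in the lumen may still be visible and scored, because the stomach was emptied at the start and nothing is suctioned at the last gastroscopy before the pictures. The offset is therefore partial.

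**Scale**

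Input: 30 patients per arm (Steps and Procedures).

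- One patient whose endoscopic score falls to 1 (no bleeding in Appendix E) changes that arm's endoscopic incidence by 1/30 = 0.033, or 3.3 percentage points.
- The plan does not say how the two sources combine or which score counts as bleeding. Assume that any image scored 2 or more makes the case positive. The same patient then changes the combined incidence by 0/30 = 0 points if any laparoscopic image is positive (case 1), and by 1/30 = 3.3 points if none is (cases 2 and 3).

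The 3.3 points are simply the weight of one patient at this sample size. They do not estimate the bias, because the documents give no rate of bleeding, cautery or suturing.

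**The case against.** The strongest reply is that little real exposure remains. A surgeon treats bleeding that can be seen. What is visible from outside is scored at 10 seconds, and what is visible only from inside is first assessed at the gastroscopy itself. The no-suction rule and the worst-picture rule both help to keep shed blood in the score. The focus on clips may be deliberate: the secondary outcome, the deferral and the form all single them out, and the form's limit to non-routine clips suggests that they also have a routine use. Nothing in the plan says that non-urgent cautery or suturing happens in this interval.

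Much of this stands. It confines the issue to the endoscopic component and to cases 1 to 3 above, and it means that a bias is possible but not shown. It does not close the gap. The endoscopic score is determined separately, retained blood need not earn the same severity score once bleeding has been stopped, and the missing form field remains whatever the reason for the clipping rule.

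A reader might go further in two ways that the documents do not support.

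- *That the gap pushes the result towards non-inferiority, since the arm that bleeds more would be treated more.* The documents give no treatment pattern, no rates and no margin, so the direction is unknown.
- *That the use of cautery or sutures could never be checked.* The plan provides for access to source data and documents, which may hold some record. What can be said is that it is not captured on the study form.

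**Conclusion.** The point holds in limited form. After the last firing the plan defers and records clipping only, so cautery or suturing before the final gastroscopy pictures is allowed and leaves no entry on the study form. That is a route by which an unmasked decision could lower the endoscopic part of the primary outcome. It does not affect laparoscopic scores already taken, and the no-suction rule partly offsets it.

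The size and direction of any bias cannot be derived. A bias between arms would need treatment in the interval, a lower score as a result, and unequal use by device. The documents establish none of these. The conclusion rests on reading the clipping sentence and the recording sentence as covering clips alone, which is what they say. Because the remedy is a small change to conduct and removes the route for non-urgent treatment, it should be made.

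**What to change.** In the gastroscopy paragraph of Steps and Procedures, replace the clipping sentence with wording such as:

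*The final gastroscopy pictures will be taken before any clipping, cautery or suturing of the staple line, unless the surgeon judges earlier treatment medically necessary. Each such instance will be recorded.*

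Add one row to Appendix C for the type of each measure (clip, suture, cautery) and its timing: before the last firing, between the last firing and the gastroscopy pictures, or after them. Keep this row off Appendix E, so that the evaluator learns nothing about treatment. The row would also capture control before the last firing, which the new sentence does not affect and which can likewise influence the later endoscopic pictures.

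The blinded score as read should remain the result. I would not add an analysis that counts treated lines as bleeds, because it would rest on the unmasked surgeon's decision.

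The cost is a brief delay to non-urgent haemostasis (the plan does not give the length of the interval) and one extra form row. Urgent treatment stays with the surgeon.
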